Trial Periods	Screening ¹	Randomised Treatment Period																Post Treatment FU		
		Loading						Maintenance										19	20 EOS ⁴	
Visit	1	2 ²	3	4	5	6	7	8	9 PE ³	10	11	12	13	14	15	16	17			18 EOT ⁴
Week	-4 to -2		1	2	3	4	8	12	16	20	24	28	32	36	40	44	48	52	60	68
Day	-28 to -14	1	8 ±2	15 ±2	22 ±2	29 ±2	57 ±7	85 ±7	113 ±7	141 ±7	169 ±7	197 ±7	225 ±7	253 ±7	281 ±7	309 ±7	337 ±7	365 ±7	421 ±7	477 ±7
Informed Consent	x																			
In/exclusion criteria	x	x																		
Demographics, BC /Medical History ⁵	x	x																		
Physical Examination ⁶	x ^C	x ^T	x ^T	x ^T	x ^T	x ^T	x ^T	x ^T	x ^T	x ^T	x ^T	x ^T	x ^T	x ^T	x ^T	x ^T	x ^T	x ^C	x ^T	x ^C
Height and weight	x																			
Vital Signs ⁷	x	x	x	x	x	x	x	x	x	x	x	x	x	x	x	x	x	x	x	x
Smoking Status / History		x							x										x	
12-lead ECG	x	x				x			x			x			x				x	
Pregnancy Testing ⁸	x _s	x _{u(s)}	x _{u(s)}	x _{u(s)}	x _{u(s)}	x _{u(s)}	x _{u(s)}	x _{u(s)}	x _{u(s)}	x _{u(s)}	x _{u(s)}	x _{u(s)}	x _{u(s)}	x _{u(s)}	x _{u(s)}	x _{u(s)}	x _{u(s)}	x _{u(s)}	x _{u(s)}	x _{u(s)}
Safety Laboratory	x	x		x		x	x	x	x	x	x		x		x		x	x	x	x
Infections Testing ⁹	x																		x	
ADA / Nab ¹¹		x		x		x	x	x	x		x		x		x		x	x	x	x
DNA banking (optional) ¹²		x																		

[figure not shown]
Proprietary confidential information © 2019 Boehringer Ingelheim International GmbH or one or more of its affiliated companies

[figure not shown]
[figure not shown]
Trial Periods	Screen- ing ¹	Randomised Treatment Period																Post Treatment FU		
		Loading						Maintenance												
Visit	1	2 ²	3	4	5	6	7	8	9 PE ³	10	11	12	13	14	15	16	17	18 EOT ⁴	19	20 EOS ⁴
Week	-4 to -2		1	2	3	4	8	12	16	20	24	28	32	36	40	44	48	52	60	68
Day	-28 to -14	1	8 ±2	15 ±2	22 ±2	29 ±2	57 ±7	85 ±7	113 ±7	141 ±7	169 ±7	197 ±7	225 ±7	253 ±7	281 ±7	309 ±7	337 ±7	365 ±7	421 ±7	477 ±7
PPP ASI / PPP SI ¹⁴	x	x	x	x	x	x	x	x	x	x	x	x	x	x	x	x	x	x	x	x
PPP PGA, [REDACTED]	x	x	x	x	x	x	x	x	x	x	x	x	x	x	x	x	x	x	x	x
[REDACTED]	x	x				x		x				x						x		
Photos of skin lesions	x	x	x	x	x	x	x	x	x	x	x	x	x	x	x	x	x	x	x	x
Pain VAS, [REDACTED]	x	x	x	x	x	x	x	x	x	x	x	x	x	x	x	x	x	x	x	x
[REDACTED]	x	x				x			x		x							x		
[REDACTED]		x							x									x		
Skin biopsy (optional) ¹⁸		x							x											
IRT call ¹⁹	x	x	x	x	x	x	x	x	x	x	x	x	x	x	x	x	x	x		
Administer study drug ²⁰		x	x	x	x	x	x	x	x	x	x	x	x	x	x	x	x	x		
Local tolerability		x	x	x	x	x	x	x	x	x	x	x	x	x	x	x	x	x		
Adverse events	x	x	x	x	x	x	x	x	x	x	x	x	x	x	x	x	x	x	x	x

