5.2.6.1.4 Adverse events of special interest

The term adverse events of special interest (AESI) relates to any specific AE that has been identified at the project level as being of particular concern for prospective safety monitoring and safety assessment within this trial, e.g. the potential for AEs based on knowledge from other compounds in the same class. AESIs need to be reported to the sponsor’s Pharmacovigilance Department within the same timeframe that applies to SAEs, please see [Section 5.2.6.2.2](#).

The following are considered as AESIs:

Systemic hypersensitivity reactions including anaphylactic reaction

Any suspicion of severe systemic hypersensitivity reaction and of any potential cases of anaphylaxis should be defined and assessed using the criteria discussed in the statement paper from Sampson HA ([Appendix 10.1, R11-4890](#)).

Severe infections (according to RCTC grading in [Appendix 10.2](#))

Opportunistic and mycobacterium tuberculosis infections

These include pneumocystis jirovecii, BK virus disease including PVAN, CMV, post-transplant lymphoproliferative disorder (EBV), progressive multifocal leucoencephalopathy, bartonellosis (disseminated only), blastomycosis, toxoplasmosis, coccidioidomycosis, histoplasmosis, aspergillosis (invasive only), candidiasis (invasive or pharyngeal), cryptococcosis, other invasive fungi (mucormycosis (zygomycosis, rhizopus, mucor, lichtheimia), scedosporium/pseudallescheria boydii, fusarium), legionellosis, listeria monocytogenes (invasive only), tuberculosis, nocardiosis, non-tuberculous mycobacterium, salmonellosis (invasive only), HBV reactivation, herpes simplex (invasive only), herpes zoster, strongyloides (hyperinfection syndrome and disseminated forms only), paracoccidioides, penicillium marneffeii, sporothrix schenckii, cryptosporidium species (chronic only), microsporidiosis, leishmaniasis (visceral only), trypanosoma cruzi infection (Chagas’ disease) (disseminated only), campylobacteriosis (invasive only), shigellosis (invasive only), vibriosis (invasive due to vibrio vulnificus), HCV progression [[R17-2617](#)].

Hepatic injury

A hepatic injury is defined by the following alterations of hepatic laboratory parameters:

- an elevation of AST (Aspartate Aminotransferase) and/or ALT (Alanine Aminotransferase) ≥ 3 fold ULN combined with an elevation of total bilirubin ≥ 2 fold ULN measured in the same blood draw sample, or
- aminotransferase (ALT, and/or AST) elevations ≥ 10 fold ULN.

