Potentially clinically significant abnormalities will be identified based on BI standard rules which are based on normalized converted lab values, i.e. using SI units. These rules will be listed in the SDL appendix of the CTR. Frequency tables will summarize the number of patients with potentially clinically significant abnormalities. Patients having an abnormal lab value at baseline will be presented separately. A separate listing will present potentially clinically significant abnormal lab values; for each functional lab group all patient's lab values will be listed, if there exists at least one lab value with clinically significant abnormality within the group.

The frequency of patients with AST or ALT elevations $\geq 3xULN$, $\geq 5xULN$, $\geq 10xULN$, and $\geq 20xULN$ will be displayed based on standardized laboratory values. To support analyses of

liver related adverse drug effects, the frequency of patients with AST and/or ALT $\geq 3xULN$ combined with a total bilirubin $\geq 2xULN$ in a 30 day period after AST/ALT elevation will be displayed, stratified by alkaline phosphatase $< 2xULN$ and $\geq 2xULN$ (a patient can potentially be in both alkaline phosphatase strata in case of multiple AST/ALT and bilirubin elevations). The start of the 30 day time span is triggered by each liver enzyme elevation above the defined thresholds. This analysis will be based on standardized laboratory values. A graphical analysis of the ALT and total bilirubin during the on-treatment period will also be performed; the so called eDISH plot. In the graph, for each subject, the peak total bilirubin is presented as a fold increase over the ULN against the peak ALT as a fold increase over the ULN, on a log10 scale. The measurements displayed of total bilirubin and ALT may, or may not, occur on the same date. Two reference lines, $2xULN$ for total bilirubin and $3xULN$ for ALT, are drawn onto the graph in order to divide the plane into four quadrants. Normal cases are in the lower left quadrant, potential DILI cases are in the upper right quadrant (Hy's Law quadrant), while the lower right quadrant is known as the Temple's corollary range (ALT $\geq 3xULN$ and total bilirubin $< 2xULN$).

Clinically relevant findings in laboratory data will be reported as baseline conditions (at screening) or as AEs (during the trial) if judged clinically relevant by the investigator, and will be analyzed as such.

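### The two combined liver displays leave a narrow gap: the AST/ALT-bilirubin table looks 30 days ahead while later labs are mostly 56 days apart, and the eDISH plot omits AST

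*SAP*

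**What the plan says.** SAP 7.8.2 plans two displays that bring aminotransferases and bilirubin together.

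- **Table.** It counts patients with AST and/or ALT of at least 3xULN combined with total bilirubin of at least 2xULN "in a 30 day period after AST/ALT elevation will be displayed, stratified by alkaline phosphatase". The span looks forward only, and it restarts: "The start of the 30 day time span is triggered by each liver enzyme elevation above the defined thresholds".
- **eDISH plot.** For each patient "the peak total bilirubin is presented as a fold increase over the ULN against the peak ALT as a fold increase over the ULN", with reference lines at 3xULN for ALT and 2xULN for bilirubin. The two peaks need not coincide: "The measurements displayed of total bilirubin and ALT may, or may not, occur on the same date". The plot is confined to the on-treatment period. AST is not plotted.

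Protocol 5.2.6.1.4 defines hepatic injury, an adverse event of special interest, as "an elevation of AST (Aspartate Aminotransferase) and/or ALT (Alanine Aminotransferase") of at least 3xULN with bilirubin of at least 2xULN in one blood draw, or an aminotransferase of at least 10xULN. The "Safety Laboratory" row of the protocol Flow Chart sets when these values are measured.

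**The concern.** A forward span of 30 days finds a delayed bilirubin rise only if a sample is taken inside it. Once labs move to 8-week spacing, no scheduled sample is. An isolated AST or ALT between 3xULN and 10xULN does not meet the protocol's hepatic injury alert, so the liver-injury checklist does not apply and a retest is left to the investigator (Protocol 6.1).

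The eDISH plot would normally pick up what the table misses, because it pairs peaks from any two on-treatment dates. It does so for ALT only, which is narrower than both the protocol definition and the SAP's own table. A patient whose injury pattern is led by AST could then be shown as a combined case nowhere. In a trial of about 140 patients, with liver injury a listed hypothetical risk (Protocol 1.4.2), a single combined case would deserve attention.

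**Working it through.** The plan gives no figure of its own to reproduce. The check compares the lab schedule with the 30-day span.

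**Inputs.** The Flow Chart places safety labs at Day 1 and Weeks 2, 4, 8, 12, 16, 20, 24, 32, 40, 48, 52, 60 and 68. Visit windows are 2 days either side at Weeks 2 and 4, and 7 days either side from Week 8 (Flow Chart; SAP Table 6.7: 1).

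**Step 1: planned intervals.** Differences of planned days give 14, 14, 28, 28, 28, 28, 28, 56, 56, 56, 28, 56, 56. That is 13 intervals: two of 14 days, six of 28 and five of 56. Patients entering the extension have no Week 60 or 68 visit (SAP Table 6.7: 1, note D). For them there are 11 intervals, three of them 56 days.

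**Step 2: allowed range.** Range = planned interval plus or minus the sum of the two windows.

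| Interval | Range (days) | Next scheduled lab within 30 days? |
|---|---|---|
| 14 days (Day 1 to Week 2; Week 2 to 4) | 12 to 16; 10 to 18 | always |
| 28 days, Week 4 to 8 | 28 ± 9 = 19 to 37 | depends on visit dates |
| 28 days, the other five | 28 ± 14 = 14 to 42 | depends on visit dates |
| 56 days (all five) | 56 ± 14 = 42 to 70 | never |

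**Step 3: share of intervals whose next scheduled sample falls within 30 days.** Assume visit days are uniform and independent over their windows; the documents do not say this. A 28-day interval exceeds 30 days when the second visit's deviation is more than 2 days above the first's.

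- Both windows 7 days: 15 × 15 = 225 pairs, of which 12 + 11 + … + 1 = 78 exceed 30 days. Within 30 days: 147/225 = 65.3%.
- Week 4 to 8: 5 × 15 = 75 pairs, of which 7 + 6 + 5 + 4 + 3 = 25 exceed. Within 30 days: 50/75 = 66.7%.
- All 13 intervals: 2 + 0.667 + 5 × 0.653 = 5.93, and 5.93/13 = 46%.
- From Week 24 on: 0.653/6 = 11%. For extension entrants: 0.653/4 = 16%.

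These are shares of lab intervals. They are not proportions of liver cases missed.

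**Step 4: which patients fall out of both displays.** AST, ALT and bilirubin belong to the same laboratory panel, and each enzyme elevation restarts the span. Take AST 4xULN and ALT 2.5xULN at Week 32 (Day 225), with bilirubin below 2xULN, and then bilirubin 2.5xULN at Week 40 (Day 281). The gap is 281 − 225 = 56 days.

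- If AST is still at least 3xULN at Week 40, that sample starts its own span and the patient is in the table, provided same-day bilirubin counts.
- If ALT reaches 3xULN at any on-treatment sample, the patient is in the upper right eDISH quadrant.
- If AST is back below 3xULN at Week 40, ALT never reaches 3xULN and no unscheduled sample is taken, the patient is in neither display as a combined case.

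With the larger of ALT/ULN and AST/ULN on the horizontal axis, the third patient plots at 4 and 2.5, in the upper right quadrant.

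**The case against.** A reader might infer that any AST-led case with a bilirubin rise at the next scheduled lab is missed by both displays. The documents do not support this. Because the span restarts at every elevation, persistent AST is captured in the later sample, and ALT-led late cases reach the eDISH quadrant. A reader might also take the 46% and 11% as rates of missed cases, but they ignore same-sample bilirubin, persistent AST, the plot and any retest.

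The other side has further points that stand:

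- The values are not lost. The patient is in the AST/ALT frequency table at 3xULN and above, all individual laboratory data are listed with out-of-range values flagged (SAP 7.8.2), and an independent committee reviews unblinded safety data (SAP 7.10).
- Retesting visits are allowed (Protocol 6.1), clinically relevant abnormal results are reported as adverse events (5.2.3) and followed until resolved, chronic or stable (5.2.6.2.2), and hepatic symptoms prompt measurement of ALT, AST and bilirubin (5.2.6.1.4).
- The standard laboratory analyses sit in a sponsor guideline cited by the SAP but not available here, so further liver displays cannot be ruled out.
- Plotting ALT alone is a defensible choice, since AST also rises from muscle.
- Stretching the table's span to the next scheduled lab would still make counting depend on visit dates.

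What remains is that none of the provisions described in the documents labels the patient in Step 4 as a combined case. The hepatic injury definition needs both values in one draw or 10xULN, and the user-defined event concepts in SAP Table 7.8.1: 1 contain no hepatic search.

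**Conclusion.** The gap is real and narrow. In the five 56-day intervals (three for extension entrants) the table in effect captures only same-sample cases unless an unscheduled test is done. In the six 28-day intervals the next lab falls beyond 30 days only when visits drift, about a third of the time under uniform, independent visit days.

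A patient is missing from both displays as a combined case only if all of these hold: AST at least 3xULN; ALT never at least 3xULN on treatment; bilirubin first reaching 2xULN more than 30 days later; AST already below 3xULN by then; and no intervening unscheduled test. The documents give no basis for saying how often this would happen. The reading assumes that bilirubin from the same sample as the elevation counts in the table, which the SAP does not state outright.

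The displays are descriptive and no hypothesis test is affected. This is a minor improvement worth making because it is cheap and brings the plot into line with the AST and/or ALT definition used elsewhere in the plan.

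**What to change.** - **Main change.** In the eDISH plot, add an AST panel, or plot the peak of the larger of ALT/ULN and AST/ULN. Keep the restriction to the on-treatment period.
- **Optional.** Beside the 30-day table, add a supplementary count with no 30-day limit between the enzyme elevation and the bilirubin elevation. State in the SAP that same-sample bilirubin counts.

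The cost is a few lines of SAP text and minor programming. No visit, sample or change in patient management is involved. The downside is a few more cases to review, including AST rises of muscle origin. Creatine kinase is already in the safety panel (Protocol Table 5.2.3: 1) and helps to sort these.

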6. GENERAL ANALYSIS DEFINITIONS

6.1 TREATMENTS

For more details of study information on the treatment to be administered, assignment to treatment, and selection of dose, refer to Section 4 of the CTP.

The following study phases are defined:

Table 6.1: 1 Flow chart of analysis phases

Study analysis phase	Description	Start (included)	End (included)
Screening phase	Screening	Earliest of (Date of informed consent, first screening procedure)	Date/time of start of the first study dose minus 1 minute.
Loading treatment phase	On-treatment period	Date/time of start of the first study loading dose (Day 1)	Earlier of: i) Date/time of start of the first maintenance dose; or, ii) Date of end of last loading dose + 112 days at 11:59 p.m. if patient early discontinued study treatment before the first maintenance dose
Maintenance treatment phase (primary analysis at week 16)		Date/time of start of the first study maintenance dose (if applicable)	Earlier of: i) Date/time of start of the first maintenance dose at or after week 16; or, ii) Date of end of last maintenance dose + 112 days at 11:59 p.m. if patient early discontinued study treatment before week 16
Maintenance treatment phase (post primary analysis at week 16)		Date/time of start of the first maintenance dose at or after week 16 (if applicable)	Earlier of: i) Date/time of start of first dose in OLE 1368.24 trial; or, ii) Date of end of last study maintenance dose + 112 days at 11:59 p.m.
Follow-up ¹ phase (if applicable)	Off-treatment period (if applicable)	Date of end of last study dose + 113 days at 0:00 a.m.	Latest of: i) Date of EOS visit; ii) end date on trial termination page at 11:59 p.m. iii) Date/time of start of first dose in OLE 1368.24 trial;

Dates are defined individually per patient. If more than one date is associated with a specific visit, measurements associated with a specific date are assigned to a study analysis phase according to the rules specified in the table. An analysis phase will not extend beyond the start date of the following phase.

¹ The off-treatment period (i.e. Follow-up phase) only exists if the trial completion date is after the date of end of last administration + 112 days.

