7.8 SAFETY ANALYSIS

All safety analyses will be performed following BI standards. No hypothesis testing is planned. OC-IR and OR methods will be used for safety reporting.

In primary analysis, AE and possibly clinically significant laboratory abnormalities up to week 16 will be analyzed. In final analysis, AE and possibly clinically significant laboratory abnormalities up to and post the first maintenance treatment at or after week 16 will be analyzed separately.

Primary analysis: AE and possibly clinically significant laboratory abnormalities up to week 16

The analysis will include all on-treatment events up to the treatment at week 16 based on SAF. If patient early discontinued from treatment prior to week 16 or missed week 16 treatment, then the on-treatment events up to Day 127 (the right limit of the extended week 16 visit window) will be included.

Final analysis: AE and possibly clinically significant laboratory abnormalities prior to the first maintenance at or after week 16

The analysis will include on-treatment events up to the first maintenance treatment at or after week 16 based on SAF. If a patient early discontinued from treatment prior to week 16, then the patient's events up to the end of REP of the last treatment will be included.

One additional group will be reported for AE and possibly clinically significant laboratory abnormalities, which is the combination of Arm 1, 2, 3 and 4 ("Speso Total").

Final analysis: AE and possibly clinically significant laboratory abnormalities post the first maintenance at or after week 16

The analysis will include on-treatment events post the first maintenance treatment at or after week 16 based on SAF-post 16. Only patients who have received at least one dose of treatment at or after week 16 will be included.

For AE and possibly clinically significant laboratory abnormalities, except for 5 treatment arms of the trial, one additional group will be reported which is the combination of Arm 1, 3 and 5 [REDACTED]

As the onset time of an AE will not be collected in the trial, any AE which occurs on the same day as a treatment dose will be assigned to the "post treatment". For safety assessments by visits, if time is not collected, data on the same day of a treatment dose will be treated to be "prior treatment" except for scheduled local tolerability and post-dose vital signs assessments.

Off-treatment data will be listed only

Additional analyses on AE will be also included:

AE within loading stage

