
For AE, the additional safety tables for loading dose stage will be produced by re-grouping patients based on their loading doses [REDACTED] using SAF. The outputs

will include on-treatment data up to the first maintenance dose at week 8. If patient early discontinued from treatment prior to week 8 or missed treatment at week 8, then the safety data up to Day 71 (the right limit of the extended time window of week 8) will be included:

- Overview on TEAE
- TEAE by SOC, preferred term
- Serious TEAE
- All AESI
- UDAEC

AE over on-treatment period

In the final analysis, the additional selected tables for the overall period will be produced based on SAF to report AE occurring during whole treatment period from Day 1. Note that only Arm 1-4 will be reported:

- Overview on TEAE
- TEAE by SOC, preferred term
- Serious TEAE
- All AESI
- UDAEC

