7.8.2 Laboratory data

The analyses of laboratory data will be descriptive in nature and will be based on BI standards (8). Note that data from the central Laboratory will be used for all displays described below, unless otherwise specified.

For continuous safety laboratory parameters, normalized values will be derived. Normalisation means transformation to a standard unit and to a standard reference range. The process of normalisation, handling of repeat values at the same visit for by-visit displays, as well as standard analyses for safety laboratory data are described in the BI guidance for the Display and Analysis of Laboratory Data (8). All analyses considering multiple times of the ULN (as described below) will be based on standardized and not normalized values. For continuous safety laboratory parameters, differences to baseline will be calculated. For all outputs, the last assessment before the first randomized treatment at Day 1 is chosen as the baseline value.

Only patients with at least one available post-baseline value will be included in the analysis of an individual laboratory parameter. All individual laboratory data will be listed. Values outside the reference range will be flagged.

Descriptive statistics of laboratory values and for the difference from baseline on-treatment (see Section 6.7) will be based upon standardized values and provided by visit. In primary analysis, all visits up to week 16 will be reported including summaries of the last value, the minimum value and the maximum value up to week 16 based on SAF. In final analysis, all visits will be reported including summaries of the last value, the minimum value and the maximum value on treatment period for Arm 1-4 and, up to and post the first treatment at or after week 16 respectively for Arm 5 based on SAF.

Laboratory values will be compared to their reference ranges; shift tables will be provided for the number of patients with a specific RCTC grade at baseline versus the grade at the last measurement, as well as the worst grade. In particular, for shift tables in final analysis, the last measurement and the worst graded will be counted by the period up to and post the first treatment at or after week 16 respectively for Arm 5.

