7.8.3 Vital signs

The analyses of vital signs (blood pressure, pulse rate), body temperature, and body weight will be descriptive in nature. In primary analysis, descriptive statistics of vital signs and for the difference from baseline (see [Section 6.7](#)) up to week 16 will be provided based on SAF, including the last value, the minimum value and the maximum value up to week 16. In final analysis, descriptive statistics of vital signs and for the difference from baseline (see [Section 6.7](#)) for all visits will be provided based on SAF, including the last value, the minimum value and the maximum value on treatment for Arm 1-4 and, up to and post the first treatment at or after week 16 respectively for Arm 5.

Clinically relevant findings in vital signs data will be reported as baseline conditions (at screening) or as AEs (during the trial) if judged clinically relevant by the investigator, and will be analysed as such.

[figure not shown]

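### In the final analysis the eDISH plot gives each Arm 5 patient one point from whole-period peaks, which can mix placebo and spesolimab values

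*SAP*

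**What the plan says.** SAP Section 7.8.2 describes the plot: "A graphical analysis of the ALT and total bilirubin during the on-treatment period will also be performed". Each patient contributes one point, peak bilirubin against peak ALT, both as multiples of the upper limit of normal (ULN). The text notes that the two values need not share a date. Reference lines at 3xULN for ALT and 2xULN for bilirubin mark off the Hy's Law quadrant.

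SAP Table 6.1: 1 defines the on-treatment period as three consecutive phases: loading, maintenance to Week 16, and maintenance after Week 16. It starts on Day 1 and ends 112 days after the last dose, or at the first open-label dose if that is earlier. Under SAP Sections 6.1 and 6.3, Arm 5 receives placebo before Week 16 and spesolimab from then on.

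Other final-analysis safety outputs treat Arm 5 differently:

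- Last, minimum and maximum laboratory values (Section 7.8.2) cover the on-treatment period for Arms 1 to 4, but are given "up to and post the first treatment at or after week 16 respectively for Arm 5 based on SAF".
- In the Arm 5 shift tables (Section 7.8.2), "the last measurement and the worst graded will be counted by the period up to and post the first treatment" at or after Week 16.
- Vital-sign extremes (Section 7.8.3) are given "up to and post the first treatment at or after week 16 respectively for Arm 5".
- Under Section 7.8, "AE and possibly clinically significant laboratory abnormalities up to and post the first maintenance treatment at or after week 16 will be analyzed separately".
- For the adverse event tables over the whole treatment period (Section 7.8): "Note that only Arm 1-4 will be reported".

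Two further liver outputs in Section 7.8.2 state no analysis period: the AST/ALT xULN frequency table, and the table of bilirubin elevation "in a 30 day period after AST/ALT elevation".

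**The concern.** A peak is a maximum, and for Arm 5 the SAP splits every other maximum in this part of the plan at the switch. The eDISH peaks instead use the unsplit on-treatment period. For an Arm 5 patient who switches, the single point may be all placebo, all spesolimab, or one coordinate from each. A higher placebo-phase peak can also displace a lower elevation that arose on spesolimab.

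Drug-induced liver injury is the first hypothetical risk in the table in Protocol Section 1.4.2, and hepatic injury is an adverse event of special interest (AESI). The eDISH plot sorts patients into the Hy's Law quadrant. A reader who sees an Arm 5 point there, or beyond the ALT line, needs to know which treatment produced it, and the figure would not say.

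**Working it through.** **Text check.** The SAP states no figure to reproduce, so the first step compares the period that each final-analysis output uses for Arm 5.

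| Output | Period for Arm 5 |
|---|---|
| Laboratory last, minimum, maximum | Split at first treatment at or after Week 16 |
| Last and worst RCTC grade | Split |
| Vital-sign last, minimum, maximum | Split |
| AEs, possibly clinically significant laboratory abnormalities | Split |
| Whole-period AE tables | Arm 5 left out |
| eDISH peaks | On-treatment period, no split |
| AST/ALT xULN table, 30-day table | No period stated |

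For the maxima, Section 7.8.2 itself sets the on-treatment period (Arms 1 to 4) against the split (Arm 5). The same term used for eDISH therefore reads as the unsplit window.

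**Scheduled draws.** These come from the safety-laboratory row of the Protocol Flow Chart, post-baseline, at nominal days. Blood is drawn before dosing (Protocol Section 6.2.2), so the Week 16 draw belongs to placebo.

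- Placebo phase: Weeks 2, 4, 8, 12, 16 = 5 draws.
- Spesolimab phase: Weeks 20, 24, 32, 40, 48, 52, 60, 68 = 8 draws. Patients who enter the open-label trial skip Weeks 60 and 68, leaving 6.

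**Possible eDISH pairs** (ALT draw x bilirubin draw).

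- All pairs: 13 x 13 = 169. Straddling the switch: 2 x 5 x 8 = 80.
- Open-label entrants: 11 x 11 = 121. Straddling: 2 x 5 x 6 = 60.
- Largest gap between the two values: Day 477 - Day 15 = 462 days.

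**30-day table, for contrast.**

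- Same-visit pairs: 13. Next-visit pairs within 30 days: 7 (Weeks 2-4, 4-8, 8-12, 12-16, 16-20, 20-24, 48-52). Total 13 + 7 = 20.
- Straddling: 1 (Week 16 to Week 20, 28 days).
- Open-label entrants: 11 + 7 = 18, of which 1 straddles.

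These are counts of possible pairs, not probabilities that a case occurs.

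**Expected number of points.** The documents give no ALT rate. Assume that 1% to 5% of patients reach ALT >=3xULN with no drug effect.

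- Arm 5 points beyond the ALT line: 40 x 0.01 = 0.4 to 40 x 0.05 = 2.0.
- Placebo share of the observation: 16/68 weeks = 24% to 5/13 draws = 38%.
- Points arising in the placebo phase: 0.4 x 0.24 = about 0.1 to 2.0 x 0.38 = about 0.8.

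Points in the Hy's Law quadrant would be rarer still.

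**The case against.** The strongest reply is that the eDISH text names neither Arm 5 nor the final analysis, and that the on-treatment period often serves in the SAP as a filter against off-treatment data. Section 7.2 uses that wording for concomitant therapy and still reports the final analysis in two parts. Section 6.7 takes laboratory maxima within a period of interest, so a programmer might feed the split Arm 5 maxima into the plot. The sponsor's laboratory guidance or the ADS Plan might also say so. This does not remove the problem. Section 7.2 splits because it says so explicitly, whereas the period named for eDISH is the on-treatment period itself. The guidance and the ADS Plan are not among the documents, so a split there can be neither confirmed nor excluded.

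A pooled Arm 5 display could carry the label *Placebo & Speso* from Section 6.1. That would disclose the mixing but would not say which treatment produced the peak. Nor is a whole-period peak ever below either phase's peak, so pooling cannot remove a patient from beyond a reference line. It can still hide the spesolimab-phase value behind a higher placebo one.

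The argument on materiality largely stands. Safety analysis is descriptive. All individual laboratory values are listed, and Arm 5 maxima and worst grades are already split. The combined AESI criterion in Protocol Section 5.2.6.1.4 needs both values from one blood draw, so a cross-phase pair cannot meet it. The 462-day gap is a limiting case: Day 477 equals nominal last dose Day 365 + 112, so a Week 68 draw one day late would be off-treatment. Protocol Section 3.3.3 also excludes patients with AST or ALT above 2xULN at screening.

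**Conclusion.** The concern holds. As written, the final-analysis eDISH plot lets an Arm 5 switcher's single point mix placebo and spesolimab values, or show a placebo-only peak, while comparable outputs separate the phases or leave Arm 5 out. At most 40 of 140 planned patients are concerned, fewer if some stop before Week 16.

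The practical effect is small. On the assumed ALT rates, fewer than one placebo-phase point would lie beyond the 3xULN line. The result is a potentially misleading descriptive figure; no liver case is lost, and the Week 16 analysis is unaffected. The conclusion rests on reading the eDISH period through Table 6.1: 1 and on no split being supplied in documents not seen here. For the xULN and 30-day tables, which are not peak-based, the SAP is only silent.

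**What to change.** Add one sentence to SAP Section 7.8.2: in the final analysis, Arm 5 eDISH peaks are derived separately up to and after the first treatment at or after Week 16, and plotted under the existing Section 6.1 labels *Placebo* and *Speso post placebo*. For consistency, state the same split for the AST/ALT xULN table and the 30-day ALT/bilirubin table.

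The period split is already needed for the Arm 5 maximum-value and shift tables, so little extra programming follows. The one drawback is that each switching Arm 5 patient appears as two points, which a footnote can explain.
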